6.4.3 Exploratory Endpoint Analyses

6.4.4 Subgroup Analyses

6.5 SAFETY ANALYSES

6.5.1 Extent of Exposure

Extent of exposure to study drug will be summarized descriptively for the total dose received per patient (mg) and relative dose intensity.

- Total dose (mg): the sum of all actual doses of the study drug
- Relative dose intensity (RDI) in % is defined as:

$$100 \times \frac{\text{Total Dose (mg)}}{\text{Planned Dose Level (mg/kg)} \times \text{Weight}}$$

where planned dose level equals to 5 mg/kg, 15 mg/kg or 30 mg/kg according to treatment arm assignment. For patients in placebo arm, the planned dose level is set to 15 mg/kg. The weight is based on a patient's actual body weight on the day of drug administration.

The number (percentage) of patients requiring treatment interruption because of AEs will be summarized. Reasons for dose interruption will be summarized as well.

Patient data listings will be provided for all dosing records and for calculated summary statistics.

6.5.2 Adverse Events

The AE verbatim descriptions (investigator's description from the eCRF) will be coded using MedDRA. AEs will be coded to MedDRA lowest level term, preferred term, and primary system organ class.

A TEAE is defined as an AE that had an onset date or a worsening in severity from baseline (pretreatment) on or after the administration of study drug and up to the 30 days after dosing.

The incidence of TEAEs will be reported as the number (percentage) of patients with TEAEs by system organ class and preferred term. A patient will be counted only once by the highest severity grade per NCI-CTCAE Version 5.0 within a system organ class and preferred term, even if the patient experienced more than 1 TEAE within a specific system organ class and preferred term. The number (percentage) of patients with TEAEs will also be summarized by relationship to the study drug.

Treatment-related TEAEs include those events considered by the investigator to be related to study treatment or with missing assessment of the causal relationship. SAEs, deaths, \geq Grade 3 TEAEs, treatment-related TEAEs, and TEAEs that led to treatment discontinuation or treatment interruption will be summarized.

An overview table of patients with at least one TEAE will be presented with the incidence of:

- patients with any TEAE
- patients with any TEAE with grade 3 or higher
- patients with any serious TEAE
- patients with any TEAE leading to death
- patients with any TEAE leading to treatment discontinuation
- patients with any TEAE leading to drug interruption
- patients with any TEAE leading to infusion rate decreased

- patients with any treatment-related TEAE
- patients with any treatment-related TEAE with grade 3 or higher
- patients with any treatment-related serious TEAEs

-
- patients with any treatment-related TEAE leading to death
 - patients with any treatment-related TEAE leading to treatment discontinuation
 - patients with any treatment-related TEAE leading to drug interruption
 - patients with any treatment-related TEAE leading to infusion rate decreased

Treatment-related AEs also include those events with missing assessment of the causal relationship.

The incidence of following TEAEs will be reported by SOC and PT, sorted by decreasing order of the frequency of the SOC first and then by decreasing order of the frequency of the PT within the SOC:

- patients with any TEAE
- patients with any serious TEAE
- patients with any TEAE leading to death
- patients with any TEAE leading to treatment discontinuation
- patients with any TEAE leading to drug interruption
- patients with any treatment-related TEAE

A patient will be counted only once by the highest grade according to NCI-CTCAE, version 5.0, within a SOC and PT, even if the patient experienced more than one TEAE within a specific SOC and PT.

The incidence of following TEAEs will be reported by SOC, PT and Worst Grade:

- patients with any TEAE
- patients with any treatment-related TEAE

Subject data listings of all AEs, SAEs, treatment-related AEs, grade 3 or above AEs, AEs that led to death and AEs that led to treatment discontinuation, dose interruption will be provided.

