4.1. Inclusion Criteria

Each patient must meet all of the following inclusion criteria to be considered eligible for participation in this study:

1. Participant must be at least 18 years of age at the time of signing the informed consent.
2. Laboratory-confirmed SARS-CoV-2 infection (positive reverse transcription-polymerase chain reaction [RT-PCR] test or other testing methods authorized by local regulatory authorities) in any samples following local practice ≤ 72 hours prior to screening
3. Have experienced COVID-19 symptoms for ≤ 7 days prior to treatment assignment, such as fever, cough, shortness of breath, sore throat, diarrhea, vomiting, and dysgeusia
4. Agree to the collection of nasopharyngeal swabs, saliva, and venous blood
5. Female patients of childbearing potential must be willing to use a highly effective method of birth control (see [Appendix 4](#)) from the time of study enrollment until 4 months after the study dosing
6. Male patients with female partners of childbearing potential must be willing to use a highly effective method of birth control (see [Appendix 4](#)) from the time of study enrollment until 4 months after the study dosing
7. Able to provide written informed consent and can understand and agree to comply with the requirements of the study and the schedule of assessments

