7.4. Follow-up Period

The follow-up period starts from the next day following the infusion of the study drug through Day 113 (± 7 days). Safety, efficacy, PK, immunogenicity, and biomarker assessments will be performed during the follow-up period as described in [Appendix 1](#) and [Appendix 2](#).

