9.6. Timing, Frequency, and Method of Capturing Adverse Events and Serious Adverse Events

9.6.1. Adverse Event Recording Period

After informed consent has been signed but before the administration of the study drug, only SAEs should be reported.

After initiation of the study drug, all AEs and SAEs, regardless of relationship to study drug, will be reported until 30 days after study treatment or End-of-Study Visit, whichever is later. After the period, the investigator should report any SAEs that are considered to be related to the study drug.

For the follow-up period for AEs, see Section [9.3.4](#).

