- b Telehealth/remote nurse home visits will be permitted after Day 1 visit (treatment)/discharge from the hospital if circumstances prevent visits to the clinic. Day 5, Day 22, and Day 57 visits will be performed by phone/video.
- c The EOS Visit will be conducted within 7 days after a premature study discontinuation. The Day 113 visit is the EOS Visit for patients who complete all the previously planned study visits.
- d The Safety Follow-up Visit is only for patients who prematurely discontinue the study within 30 days after study treatment. The Safety Follow-up Visit will be conducted at 30 days (\pm 3 days) after study treatment (Day 31 [\pm 3 days]). If the premature discontinuation from study occurs within 7 days prior to Day 31 (\pm 3 days), the Safety Follow-up Visit can be combined with the EOS Visit or the Day 29 visit, as appropriate.
- e Written informed consent must be obtained before performing any study-specific procedures. Consent must be obtained using the current version of the form approved by the Independent Ethics Committee (IEC)/Institutional Review Board (IRB). The consent can be obtained via remote consent if approved by local IRB.
- f Follicle-stimulating hormone (FSH) and estradiol assessments will be performed in female patients who are $<$ 55 years of age with no spontaneous menses for \geq 12 months to identify the status of no childbearing potential (refer to [Appendix 4](#)). Historical test results are allowed.
- g Positive results of SARS-Co V-2 test (RT-PCR or other tests authorized by local regulatory authorities) \leq 72 hours prior to screening are required for confirmation of eligibility.
- h Patients enrolled will be randomized via IRT to receive placebo, BGB-DXP593 5 mg/kg, BGB-DXP593 15 mg/kg, or BGB-DXP593 30 mg/kg on Day 1.
- i The dose of BGB-DXP593 will be based on the patient's actual body weight on the day of receiving the study drug (Day 1).
- j Vital signs will be monitored approximately every 15 minutes during the infusion, and then hourly till 2 hours after the infusion; the monitoring will include measurements of body temperature ($^{\circ}$ C), pulse rate, respiratory rate, saturation of oxygen (SpO₂), and blood pressure (systolic and diastolic). Pulse rate and blood pressure will be measured while the patient is in a seated or supine position after resting for 10 minutes. Height will be measured at screening only and weight will be measured at Day 1 before study drug dosing.

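### AEs are collected to Day 113, but every specified AE incidence table stops 30 days after dosing, and the window for SAE and death summaries is unclear

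*SAP*

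**What the plan says.** **Collection.** Protocol 9.6.1 requires that, once study drug has started, all AEs and SAEs, whatever their relationship to the drug, "will be reported until 30 days after study treatment or End-of-Study Visit, whichever is later". Appendix 1 (footnotes to the schedule) fixes the later limit: "The Day 113 visit is the EOS Visit for patients who complete all the previously planned study visits". Protocol 7.4 agrees: "The follow-up period starts from the next day following the infusion of the study drug through Day 113".

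**Definition.** Protocol 10.3.2 and SAP 6.5.2 use the same TEAE window, with onset or worsening "on or after the administration of study drug and up to the 30 days after dosing".

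**Tables.** SAP 6.5.2 specifies three groups of AE tables: an overview, incidence by system organ class and preferred term, and incidence by worst grade. All the rows are TEAE rows. The serious-event row, for example, is "patients with any serious TEAE", and the fatal-event row is likewise limited to TEAEs.

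**A sentence that reads more widely.** The same SAP section also says: "SAEs, deaths, \geq Grade 3 TEAEs, treatment-related TEAEs, and TEAEs that led to treatment discontinuation or treatment interruption will be summarized". Here SAEs and deaths carry no TEAE qualifier, but Grade 3 or higher events do.

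**Listings.** The AE listings at the end of SAP 6.5.2 cover all AEs, with no time limit.

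**The concern.** Safety is the first secondary objective. The trial asks sites to record every AE for about 16 weeks, but the specified incidence tables use only the first 30 days. An imbalance between the dose arms and placebo that arose later in non-serious AEs, including non-serious Grade 3 or higher events, would have to be found by reading patient listings. Listings do not give counts or percentages by arm.

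The position for SAEs and deaths is different but also unsatisfactory. Two programmers working from SAP 6.5.2 could produce different tables. One would follow the general sentence and count SAEs and deaths to the End-of-Study Visit. The other would follow the specified rows and stop at 30 days. The secondary endpoint in Protocol 2.2.2 and SAP 4.2 names SAEs separately from TEAEs, which favors the wider reading, but no text settles it.

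The protocol synopsis also commits to describing all safety data by actual treatment arm. TEAE-only tables do not deliver that for AEs that start after the window, and SAP Section 8 declares no change from the planned analysis.

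**Working it through.** The documents state no share of follow-up, so the first step is to confirm their day count.

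**Inputs**
- End-of-Study Visit for a completer: Day 113, ±7 days (Protocol 7.4, Appendix 1).
- Day 113 in hours after the start of infusion: 2688; Day 29: 672 (Appendix 2).
- 30 days after treatment is Day 31 (Protocol 7.4.2).
- TEAE window: 30 days after dosing (SAP 6.5.2).

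**Day count.** Day d is d − 1 days after dosing.
- Day 113: (113 − 1) × 24 = 2688 h, matching Appendix 2, so 112 days.
- Day 29: (29 − 1) × 24 = 672 h, also matching.
- 30 days after dosing: 30 + 1 = Day 31, matching Section 7.4.2.

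**Share of AE collection outside the TEAE window.** Share = (days collected after dosing − 30) / days collected after dosing.

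| Final visit | Days collected | Days outside | Share |
|---|---|---|---|
| Day 106 (earliest) | 105 | 75 | 71.4% |
| Day 113 (nominal) | 112 | 82 | 73.2% |
| Day 120 (latest) | 119 | 89 | 74.8% |

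Counting study days inclusively gives 82/113 = 72.6%.

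**Patient-time, as a ceiling.** If all 172 planned patients were dosed and completed, the time outside the window would be 172 × 82 / 365.25 = 38.6 patient-years, out of 172 × 112 / 365.25 = 52.7. Any dropout lowers both figures. A patient who leaves the study by Day 31 has AE collection to about Day 31 only, so little or nothing is lost.

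**What happens to an event that starts after Day 31**

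| Event | General sentence, SAP 6.5.2 | Specified rows, SAP 6.5.2 | Result |
|---|---|---|---|
| Non-serious AE, Grade 1–2 | not covered | TEAE only | listing only |
| Non-serious AE, Grade 3 or higher | TEAE only | TEAE only | listing only |
| SAE | no TEAE limit | TEAE only | ambiguous |
| Death | no TEAE limit | TEAE only | ambiguous |

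The efficacy section does not resolve the last row. SAP 6.4.2 reports the all-cause mortality rate at Day 29. Protocol 10.2.2 plans a Kaplan-Meier analysis of mortality censored at the last date known alive, but the SAP's version reports only the Day 29 rate.

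**Other safety data.** SAP 6.5.4 presents vital signs at all visits. SAP 6.5.3 takes laboratory shifts to the worst postbaseline grade. Neither has a 30-day limit.

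**The case against.** The strongest reply is that nothing here is inconsistent. Protocol and SAP agree on the TEAE window. The same 30 days governs concomitant medications (Protocol 10.1.5), the Safety Follow-up Visit after early discontinuation (7.4.2) and pregnancy reporting (9.6.5). Collecting for longer than one tabulates, and listing the rest, is a recognizable choice in a Phase 2 study of about 172 patients. **This stands as a defense of the definition**, which need not change. It does not explain why late AEs should go without a by-arm count, nor which window applies to SAEs and deaths.

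The second reply is that 73% measures time, not information. **This stands.** No figure in the documents shows how many events would start late. AE checks also appear sparser then: as far as the Appendix 1 grid can be read, only Days 85 and 113 are scheduled AE assessments after Day 31.

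Three stronger readings are tempting, and the documents do not support them:
- *That about 73% of safety follow-up never enters a by-arm table.* Vital signs and laboratory summaries are not cut at 30 days, and ADA incidence (SAP 6.7) has no such limit either.
- *That late SAEs and deaths will definitely go untabulated.* The general sentence in SAP 6.5.2 promises to summarize both without the TEAE limit.
- *That waning antibody makes late antibody-dependent enhancement a particular risk.* Protocol 1.4 lists suboptimal titres among the proposed circumstances, but says these are very rarely implicated and that this antibody is unlikely to cause enhancement. No passage ties waning levels to late risk.

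Contraception "until 4 months after the study dosing" and PK and ADA sampling at Day 113 show that the protocol looks past 30 days for other purposes. They do not define a period for attributing AEs, so they are context only. The lung prediction over 29 days in Protocol 1.3.1 covers almost the same horizon as the TEAE window and does not show it to be too short.

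**Conclusion.** The gap is real and limited. For a completer, AEs that start in the last 82 of 112 days of collection (73%; 71% to 75% across the Day 113 visit window) fall outside every AE incidence table the SAP specifies. Non-serious events in that period, including Grade 3 or higher, reach listings only on any reading of the text. For SAEs and deaths the defect is ambiguity, not a demonstrated omission.

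The percentage rests on completing follow-up to the End-of-Study Visit and on counting calendar time. It says nothing about the number or importance of late events. The 30-day TEAE definition is not an error. This is a cheap improvement: the data will already exist, and by-arm tables are what would let the trial compare late safety with placebo.

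**What to change.** Keep the 30-day TEAE definition and all the TEAE tables as they are. In SAP 6.5.2:

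1. Add by-arm incidence tables, in the Safety Analysis Set by actual treatment, covering dosing to the End-of-Study Visit, for all AEs, SAEs, Grade 3 or higher AEs and deaths.
2. State the time window of every AE table, and say explicitly that the general commitment to summarize SAEs and deaths is met by the longer-window tables.

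For completers, this takes AE collection time outside the by-arm incidence tables from 82 of 112 days to none.

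Extending the TEAE definition itself is not needed. It would change a term fixed in the protocol that underlies a secondary endpoint.

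**Cost.** A few repeat tables from existing programs, with no new data. The longer window will bring in more background events, but the placebo arm is the comparator for these.

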6.5.3 Laboratory Values

Clinical laboratory (eg, hematology, clinical chemistry, coagulation, and urinalysis) values will be evaluated for each laboratory parameter as appropriate. Reference (normal) ranges for laboratory parameters will be provided.

Laboratory parameters are graded by NCI-CTCAE Version 5.0 or higher and will be summarized through shift tables from baseline to the worst postbaseline grade. Grade 3 or 4 laboratory toxicity will be summarized, and parameters with NCI-CTCAE grading in both high and low directions will be summarized separately.

6.5.4 Vital Signs

Descriptive statistics for vital sign parameters (systolic and diastolic blood pressure, SpO₂, respiratory rate, pulse rate, and body temperature) and changes from baseline will be presented by visit for all visits. Vital signs will be listed by patient and visit.

6.6 PHARMACOKINETIC ANALYSES

The following analysis plan provides the framework for the summarization of the PK data from study BGB-DXP593-102. The objective is to assess BGB-DXP593 PK and characterize PK parameters following a single IV dose. The PK analyses will be based on the BGB-DXP593 PK analysis set. Additional PK analyses (such as modeling and simulation using nonlinear mixed effects modelling) may be conducted if deemed necessary and will be described in a separate analysis plan.

6.6.1 Calculation of Serum Pharmacokinetic Parameters

Actual dose and blood draw times will be used to calculate the PK parameters. Parameters will be listed individually and summarized by dose level using descriptive statistics.

The following plasma PK parameters will be calculated for BGB-DXP593, as appropriate for the data collected. Other PK parameters may be calculated if supported by the data.

Calculation and presentation of PK parameters will be based on the Work Instruction: Best Practice Guidance: Non-Compartmental Pharmacokinetic Data Analysis for Clinical Studies, Version 1.0, Document Number VV-QDOC-13140.

Parameter (Units)	Definition	Method of Determination
AUC ₀₋₂₉ (µg·hr/mL)	Area under the serum concentration versus time curve from 0 to Day 29	Calculated using the linear up/log down variant of the trapezoidal rule
AUC _{inf} (µg·hr/mL)	AUC from zero to infinite time with extrapolation of the terminal phase	Calculated using the linear up/log down variant of the trapezoidal rule
AUC _t (µg·hr/mL)	AUC from time zero to time t	Calculated using the linear up/log down variant of the trapezoidal rule
C _{max} (µg/mL)	Maximum observed drug concentration during a dosing interval	Observed value
t _{max} (h)	Time to reach C _{max}	Actual elapsed time for observed C _{max} in each period.
t _{1/2} (hr)	half-life	ln(2)/λ _z , where λ _z is the first-order rate constant of drug associated with the terminal portion of the curve
CL (L/h)	clearance	Calculated as Dose/AUC _{inf}
V _z (L)	volume of distribution during the terminal phase	Calculated as CL/λ _z , where λ _z is the first-order rate constant of drug associated with the terminal portion of the curve

6.6.2 Reporting of Pharmacokinetic Concentrations for Descriptive Statistics

The PK analyst will appropriately flag and annotate treatment of any anomalous concentrations, exclusions and any special treatment for descriptive statistics and plots. BGB-DXP593 concentration and time data will be listed individually and summarized by dose level using descriptive statistics.

The following conventions will be used for reporting descriptive statistics for concentration data.

- PK concentrations should be reported in listings at the same level of precision as that in the source data.
- If a concentration at a given time point is below the assay quantification limit (BLQ), the concentration shall be reported as the term “BLQ” with the lower limit of quantitation (LLOQ) defined in the footnotes. BLQ values shall be treated as zero for computation of descriptive statistics.
- If a concentration at a given time point is missing it shall be reported as a missing value. Missing values may be defined in a bioanalytical source as “NS” (no sample), “NR” (no result), “IS” (insufficient sample), etc. If missing data are not identified in the bioanalytical source (i.e., the record is missing), the reporting convention of “NS” shall be utilized.
- If the calculated mean concentration is BLQ, the mean value shall be reported in outputs (such as tables) as BLQ and SD and %CV shall be reported as ND (not determined). Minimum, median, and maximum may be reported.

6.6.3 Plots of Pharmacokinetic Concentrations

BGB-DXP593 concentration versus time data will be plotted individually and summarized graphically using arithmetic mean (\pm SD) plots by dose level. Arithmetic mean concentrations that are BLQ shall be set to "missing" for plotting on both linear scale and log-linear scale.

6.6.4 Reporting of PK Parameters for Descriptive Statistics

The PK analyst will appropriately flag and annotate treatment of any anomalous PK parameters, exclusions and any special treatment for descriptive statistics.

- All the PK parameters except t_{\max} should have at least the following summary statistics: sample size (n), mean, standard deviation (SD), coefficient of variance (CV%), median, minimum, maximum, geometric mean, geometric CV%; t_{\max} should be presented as median, range (minimum, maximum) , and sample size (n) when presenting the summary statistics.
- Geometric mean (geometric CV%) will be the default method of reporting PK parameters within in-text tables.
- For any parameters that $n \leq 2$, SD should not be presented.
- The units for all PK parameters will be provided.

- It is recognized that the number of decimals in reported concentrations, for example: “9632.94401 ng/mL” or “9.963294401 ug/mL” are highly improbable and will be queried (since bioanalytical assays generally do not have this level of precision). Usually the first-in-human dose escalation trial will provide the numerical range of PK parameters e.g. AUC range from 10 to 10,000 ng.hr/mL and C_{max} range from 1 to 1000 ng/mL.

In this scenario, for reporting PK parameters such as AUC and C_{max} , the following guidance is provided for rounding:

- If the numerical value is below 100 then one decimal place may be used e.g. 0.1 or 99.9.
- For values ranging from >100, whole numbers should be used e.g. 100 or 9999.
- If > 10,000 the clinical pharmacologist may decide on changing units e.g. from $\mu\text{g/ml}$ to mg/ml.
- For reporting times e.g. for t_{max} or $t_{1/2}$, if <1 hr use 2 decimals; time up to 24 hr should be reported to one decimal place e.g. 23.5 hr, time >24 hr should be rounded to nearest whole number e.g. 105 hr.

